Title:	Plexa Registry
Design:	Prospective, single-arm, non-randomized, multi-center registry
Purpose:	To confirm the long-term safety and reliability of BIOTRONIK’s Plexa lead, as used in conjunction with a US market released BIOTRONIK implantable cardioverter defibrillator (ICD) or cardiac resynchronization therapy defibrillator (CRT-D) pulse generator. The evaluation of safety will be based on the analysis of Plexa lead-related adverse events. The Plexa Registry will provide data to permit characterization of Plexa lead failures contributing to loss of bradycardia pacing or shock therapy. Additionally, acute and chronic Plexa lead parameters will be evaluated.
Subject Population:	Subjects who are indicated for an ICD or a CRT-D. Subjects must be successfully implanted with a compatible US market released BIOTRONIK ICD or CRT-D. Subjects can be enrolled no more than 30 days after successful implantation of the Plexa system.
Enrollment:	This registry is designed to follow 1271 subjects implanted with the Plexa system through 5 years post-implant.
Clinical Sites:	Up to 75 US sites.
Primary Endpoint:	Overall incidence of adverse events (AEs) related to the Plexa lead
Secondary Endpoints:	
 1. Incidence of each individual type of AE that contributes to Primary Endpoint 1 2. Pacing threshold, sensing, and impedance measurements for the Plexa lead through 5 years post-implant 3. Shock impedance for the Plexa lead through 5 years post-implant 4. AE rates for AEs excluded from primary safety endpoint 1, through 5 years post-implant
Clinical Events Committee Chair:	[name] State Health Center [name] Hungary
Sponsor:	BIOTRONIK, Inc. Clinical Studies Department [name] [name]

1. INTRODUCTION

1.1 NAME OF DEVICE

This protocol details the registry for BIOTRONIK's Plexa implantable cardioverter defibrillator (ICD) lead, further referred to as the Plexa lead throughout this document. Currently, the following models are FDA approved:

- Plexa SD (active fixation, DF4 connector, dual coil),
- Plexa S (active fixation, DF4 connector, single coil),
- Plexa DF-1 SD (active fixation, DF-1 connector, dual coil),
- Plexa DF-1 S (active fixation, DF-1 connector, single coil), and
- Plexa DF-1 S DX (active fixation, DF-1 connector, single coil with atrial sensing channel).

1.2 REGISTRY OVERVIEW

The purpose of this registry is to confirm the safety and reliability of the Plexa lead as used in conjunction with any compatible US market released BIOTRONIK ICD or cardiac resynchronization therapy defibrillator (CRT-D). Data will be collected from no more than 1271 subjects from implant through 5 years of follow-up.

Subjects eligible for the registry include those that have been successfully implanted with a Plexa lead and a compatible US market released BIOTRONIK ICD or CRT-D no more than 30 days prior to enrollment*. Prior to enrollment procedures, subjects will be screened to ensure eligibility and will provide written informed consent. Safety will be evaluated based on the analysis of all Plexa lead-related adverse events. Acute and chronic lead parameters for sensing, pacing thresholds, pacing impedance, and shock impedance will be evaluated for the Plexa lead.

All devices included in the registry are legally marketed and prescribed by physicians according to approved indications for use.

1.3 BACKGROUND

The Plexa Registry is designed to document the clinical experience of the Plexa ICD leads (P98023/S075, approved January 5, 2017).

The Plexa lead is a transvenous ICD lead designed for permanent right ventricular pacing, sensing, and delivery of defibrillation / cardioversion shock therapies to the heart. Plexa is the successor of the Linx^{smart} and Protego ICD lead (Linx^{smart} SD / TD P980023/S038, approved September 17, 2010; Linx^{smart} S / T P980023/S043, approved February 28, 2011; Linx^{smart} S DX P980023/S049, approved February 13, 2013; Protego S / SD / T / TD P980023/S057, approved July 3, 2014). The Linx lead family has been extensively studied in the GALAXY registry. The Protego DF4 lead is being studied in the ongoing Protego DF4 Post-Approval Registry.

* For the purpose of the Plexa registry, the date of implant will be considered day 0.

1.3.1 GALAXY Lead Registry: Clinical Experience with Linx ICD Lead

BIOTRONIK sponsored the GALAXY study, an after-market registry to confirm the long-term safety and reliability of the FDA approved Linx family of ICD leads. The GALAXY Registry is registered on clinicaltrials.gov, NCT00836589. This multi-center, prospective, non-randomized registry has been ongoing since enrollment began in January 2009 and has been closed to enrollment since November 2011. The final subject visit occurred in December 2016 and the final clinical report is pending. There were 1997 subjects enrolled in the registry, 201 of which were implanted with Linx^{smart} ICD leads.

The sensing and pacing behavior was evaluated as well as the rate of lead-related complications over the available follow-up period. As of November 3, 2015, the mean pacing threshold across all Linx family ICD lead models was 0.64 ± 0.35 V, the mean sensing amplitude was 12.79 ± 5.44 mV, and the mean lead impedance was 553.0 ± 134.9 ohms. There were 61 (3.05%) subjects who experienced a primary AE related to the Linx family ICD leads.

Details on reported ICD lead-related adverse events are provided in Table 1. The total number of subjects with an adverse event may not equal the sum of the number of subjects listed in each category because an individual subject may have experienced more than one adverse event.

Table 1: All Linx Family ICD Lead-Related Adverse Events

Adverse Event	Subjects with AE, n	% Subjects with AEs	AEs, n
Primary Endpoint AEs			
Other ICD lead related: Lead noise or oversensing	21	1.05%	21
Lead impedance out of range, low impedance, potential insulation break.	16	0.80%	16
Lead impedance out of range, high impedance, potential conductor fracture.	15	0.75%	15
Lead dislodgement (> 180 days post-implant procedure)	6	0.30%	6
Lead undersensing or loss of sensing	2	0.10%	2
Inability to defibrillate or pace	1	0.05%	1
Other ICD lead related: Noise consistent with probable fracture	1	0.05%	1
Other ICD lead related: Lead migrated	1	0.05%	1
Other ICD lead related: Tension pneumothorax	1	0.05%	1
Total Primary Endpoint AEs	61	3.05%	64
Secondary Endpoint AEs Related to the ICD Lead			
Lead dislodgement (≤ 180 days post-implant procedure)	24	1.20%	25
High pacing threshold, intermittent capture, no lead capture	13	0.65%	14
Cardiac perforation with or without tamponade	5	0.25%	6
Total Secondary Endpoint AEs (Related to ICD Lead)	42	2.10%	45
Total Primary or Secondary AEs (Related to ICD Lead)	100	5.01%	109

Total number of subjects = 1997

Figure 1 shows the calculated Kaplan-Meier actuarial graph demonstrating the freedom from all primary endpoint adverse events adjudicated by the Clinical Events Committee. Table 2 displays the associated case summary. A common, final follow-up date of November 3, 2015, is assumed for all active subjects.

The standard error (SE) for the estimated survival (freedom from primary endpoint AEs) was calculated using the method of Peto et al¹. The last adverse event occurred on day 1809, and the current estimated freedom from adverse events is 95.0% (SE 1.0%) for implant times 1809 days or longer. These estimates may change as additional follow-up data are collected.

Figure 1: GALAXY Freedom from Primary Endpoint Adverse Events (%)

[figure not shown]

Table 2: GALAXY Primary Endpoint Case Summary

Total Subjects, n	Subjects with Adverse Events, n	Censored	
		n	%
1997	61	1936	96.9%

1.3.2 Protego Lead Registry: Clinical Experience with Protego ICD Lead

BIOTRONIK is currently conducting the Protego Post-Approval Registry to confirm the long-term safety and reliability of the FDA approved Protego DF4 ICD leads. The Protego Post-Approval Registry is registered on clinicaltrials.gov, NCT02243696. This multi-center, prospective, non-randomized registry has been ongoing since enrollment began in September 2014 and has been closed to enrollment since October 2016. There have been 1695 subjects enrolled in the registry as of October 10, 2016.

As of May 31, 2016, the sensing and pacing behavior was evaluated as well as the rate of lead-related complications over the available follow-up period. The mean pacing threshold across all Protego family ICD lead models was 0.62 ± 0.34 V, the mean sensing amplitude was 15.68 ± 6.00 mV, and the mean lead impedance was 574.8 ± 122.3 ohms. There was one (0.08%) subject who experienced a primary AE reported as related to the Protego ICD lead and 16 (0.23%) subjects who experienced a secondary AE reported as possibly related to the Protego ICD lead (Table 3). No subjects experienced a secondary AE adjudicated as related to the Protego ICD lead.

Table 3: Protego ICD Lead-Related Adverse Events

Adverse Event	Subjects with AE, n	% Subjects with AEs	Number of AEs
Primary Endpoint AEs			
Lead dislodgement (> 30 days post-implant procedure)	1	0.08%	1
Total Primary Endpoint AEs	1	0.08%	1
Secondary Endpoint AEs Possibly Related to the ICD Lead			
Lead dislodgement (\leq 30 days post-implant procedure)	7	0.54%	7
High pacing threshold	3	0.23%	1
Bent connector pin noted during implant procedure	1	0.08%	1
Cardiac perforation	1	0.08%	1
Inability to extend helix during implant procedure	1	0.08%	1
Intermittent capture / no lead capture	1	0.08%	1
Lead impedance out of range, high impedance	1	0.08%	1
Lead undersensing or loss of sensing	1	0.08%	1
Total Secondary Endpoint AEs (Possibly Related to ICD Lead)	16	0.23%	16
Total Primary or Secondary Endpoint AEs (Possibly Related to ICD Lead)	17	1.30%	17

Total number of subjects = 1305

Figure 2 shows the calculated Kaplan-Meier actuarial graph demonstrating the freedom from all primary endpoint adverse events adjudicated by the Clinical Events Committee. Table 4 displays the associated case summary. A common, final follow-up date of May 31, 2016, is assumed for all active subjects.

The standard error (SE) for the estimated survival (freedom from primary endpoint AEs) was calculated using the method of Peto et al¹. The last adverse event occurred on the day of implant, and the current estimated freedom from adverse events is 99.91% (SE 0.16%) for implant times 94 day or longer. These estimates may change as additional follow-up data are collected.

Figure 2: Protego Freedom from Primary Endpoint Adverse Events (%)

[figure not shown]

Table 4: Protego Primary Endpoint Case Summary

Total Subjects, n	Subjects with Adverse Event, n	Censored	
		n	%
1305	1	1304	99.9%

1.4 DEVICE DESCRIPTION

1.4.1 Plexa Lead Description

The Plexa leads are 7.8 F transvenous, steroid-eluting, endocardial lead for use with any ICD or CRT-D. The Plexa DF-1 S and Plexa S leads have two RV sensing and pacing electrodes (distal tip and ventricular ring electrode) and one defibrillation electrode (ventricular shock coil). The Plexa DF-1 S DX lead has two RV sensing and pacing electrodes, two RA sensing electrodes, and one defibrillation electrode (ventricular shock coil). The Plexa DF-1 SD and Plexa SD leads have two sensing and pacing electrodes (distal tip and ventricular ring electrode) and two defibrillation electrodes (ventricular and superior vena cava shock coils).

These leads, in conjunction with an ICD or CRT-D device, perform the following functions:

- Sense electrical signals from cardiac tissue and conduct those signals to the ICD
- Conduct bradycardia and anti-tachycardia pacing pulses emitted from the ICD to cardiac tissue
- Conduct cardioversion / defibrillation shocks of both high and low energies from the ICD to cardiac tissue

The Plexa leads are intended for permanent placement in the right ventricle. The tip and ring electrodes form the most distal portion of the lead and provide dedicated bipolar sensing and pacing.

All Plexa leads have one shock electrode that is positioned in the right ventricle. The Plexa DF-1 SD and Plexa SD dual-coil ICD leads have an additional shock electrode for placement in the superior vena cava (SVC). All Plexa leads feature Silglide[®] surface treatment, designed to reduce the force required to maneuver the lead during the implant procedure.

All Plexa leads feature an electrically active extendable / retractable fixation helix for use in lead placement. The helix is extended and retracted by rotating the contact pin with a fixation tool. Both the fixation helix and ring electrode are comprised of a platinum / iridium alloy base with fractal iridium.

The distal tip of all Plexa leads consists of a steroid eluting collar which contains the active ingredient dexamethasone acetate (DXA). Upon exposure to body fluids, the steroid elutes from the collar. Release of the steroid is intended to decrease the inflammatory response at the contact site between the lead tip and the endocardium, thereby decreasing the elevated pacing thresholds of the endocardial lead that often occur after lead implantation.

The Plexa lead has a modified internal lead tip design, with a symmetric contact spring, and minor changes to the cut of the tip of the fixation screw as compared to the Linx^{smart} and Protego leads. Additionally, the distal region, between the proximal end of the RV shock coil and the distal end of the SVC shock coil has a twisted cable design, where the lumens of the cables (peripheral lumens) are twisted around the inner lumen of the coil (helically wound around the longitudinal axis). All five lumens are coated with a lubricant, compared to only four peripheral lumens in the Linx^{smart} and Protego leads. The color coding on the label tubing has been updated according to AAMI TIR41:2014. The steroid collar on the Plexa lead has a nominal value of 0.93 mg DXA.

1.4.2 BIOTRONIK Home Monitoring[®]

Current expert consensus advocates 3- to 6-month device evaluations either in-person or by remote monitoring for ICD or CRT-D devices².

BIOTRONIK Home Monitoring[®] is a communication system which allows the automatic transmission of diagnostic patient data from the device to the physician at any time. The technology implements the use of wireless communications to provide the physician with daily patient monitoring and trend analysis information between office follow-up visits. A block diagram of the transmission path is shown in Figure 3, and the transmission steps are described as follows:

1. Communication starts with the implant, which activates a very low power RF transmitter circuitry integrated within the pulse generator.
2. The patient's device accepts patient data from the implant and transfers this digital information using a cellular short messaging system (SMS) or telephone landline connection to a BIOTRONIK Service Center for evaluation.
3. The BIOTRONIK Service Center receives incoming data and generates a customized summary which is available to the physician online via secure Internet access, or can be forwarded to the physician via fax.

Figure 3: BIOTRONIK Home Monitoring[®] Transmission Path

[figure not shown]

BIOTRONIK conducted the TRUST study to evaluate the safety and effectiveness of BIOTRONIK Home Monitoring[®]. BIOTRONIK received FDA approval (P050023/S020, approved May 12, 2009) of the following labeling claims regarding BIOTRONIK Home Monitoring[®]:

1. BIOTRONIK Home Monitoring[®] information may be used as a replacement for device interrogation during in-office follow-up visits.
2. A strategy of care using BIOTRONIK Home Monitoring[®] with office visits when needed has been shown to extend the time between routine, scheduled in-office follow-ups of BIOTRONIK implantable devices in many patients. BIOTRONIK Home Monitoring[®] data is helpful in determining the need for additional in-office follow-up.
3. BIOTRONIK Home Monitoring[®] patients—who are followed remotely with office visits when needed—have been shown to have similar numbers of strokes, invasive procedures and deaths as patients followed with conventional in-office follow-ups.
4. BIOTRONIK Home Monitoring[®] provides early detection of arrhythmias.
5. BIOTRONIK Home Monitoring[®] provides early detection of silent, asymptomatic arrhythmias.
6. Automatic early detection of arrhythmias and device system anomalies by BIOTRONIK Home Monitoring[®] allows for earlier intervention than conventional in-office follow-ups.
7. BIOTRONIK Home Monitoring[®] allows for improved access to patient device data compared to conventional in-office follow-ups since device interrogation is automatically scheduled at regular intervals.

In current US market released BIOTRONIK ICD and CRT-D devices, BIOTRONIK Home Monitoring[®] provides event and system information similar to what is currently available during office follow-up visits. The highlighted information in the BIOTRONIK Home Monitoring[®] Quick View Summary Report, Figure 4, displays the study related follow-up data automatically transmitted on a daily basis including: battery status, pacing impedance, pacing threshold, and sensing amplitude (mean / min) for both the atrial and ventricular leads. In addition, BIOTRONIK Home Monitoring[®] provides automatic daily information on arrhythmias, lead trends, current device programming, event episodes, therapy provided, and long term data trends.

Figure 4: BIOTRONIK Home Monitoring® Quick View Summary Report

2. REGISTRY DESIGN

This multi-center, prospective, non-randomized registry is designed to gather safety data on BIOTRONIK's Plexa leads. All subjects enrolled in the registry are implanted with a US market released BIOTRONIK ICD or CRT-D pulse generator and a Plexa lead.

Potential subjects will be identified by the investigator from their general patient population. Additionally, potential subjects must satisfy the registry inclusion and exclusion criteria (Section 3.1.3 and Section 3.1.4). After successful implantation of the Plexa lead with a US market released BIOTRONIK ICD or CRT-D pulse generator, if a subject satisfies the registry inclusion and exclusion criteria, written informed consent is obtained. After informed consent has been obtained, enrollment visit data will be collected. Informed consent and enrollment visit data collection may be obtained no more than 30 days after the date of implant. Device data and any adverse events since the date of the implant of the Plexa lead active at the time of consent will be collected retrospectively at the enrollment visit.

After enrollment, any subjects who have the pulse generator explanted or Plexa lead explanted or capped must be re-implanted, or have plans to be re-implanted, with a Plexa lead connected to a US market released BIOTRONIK pulse generator to remain in the study.

After enrollment, subjects will be evaluated at 3 months post-implant, 6 months post-implant, and every 6 months thereafter for 5 years. All subjects are required to be seen in-office once between the 24 and 36 month intervals and once at the 60 month interval. For all other visits, subjects may use BIOTRONIK Home Monitoring® follow-ups to meet the study visit schedule. The option to substitute a BIOTRONIK Home Monitoring® follow-up for an in-office follow-up may begin as early as the 3 month post-implant visit. Subjects should be seen in-office if not all information required during follow-up visits as noted in Section 3.2.4 can be obtained from BIOTRONIK Home Monitoring®. Subjects without a BIOTRONIK Home Monitoring® system should be seen in-office for all intervals per the study visit schedule.

Figure 5 provides an overview of the clinical registry design. Details of subject eligibility requirements are noted in Section 3.1 and details of other registry specific procedures and data collection are noted in Section 3.2 and Section 4. Figure 6 provides the visit schedule for a subject using BIOTRONIK Home Monitoring®.

BIOTRONIK may pool data from other prospective studies to supplement the Plexa Registry population to achieve the sample size of 1271 subjects needed for the primary endpoint analysis. The data collection would need to be sufficiently similar to the Plexa Registry data collection to allow pooling of the data. If data from other studies are used, the data will come from subjects who have a US market released BIOTRONIK ICD or CRT-D pulse generator and a successfully implanted Plexa lead.

Figure 5: Registry Design Flowchart

[figure not shown]
[figure not shown]

Figure 6: Visit Schedule

* In-office visit may be performed at 24, 30, or 36 Month interval

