2.3 SAMPLE-SIZE ANALYSIS

The investigation is designed to limit the number of subjects involved while still exposing the device to a sufficiently large patient population in order to ensure a representative and statistically meaningful sample.

The estimated sample size required to evaluate primary endpoint 1 is based on a superiority comparison of the overall Plexa lead AE-free rate to 92.5% at 5 years. The sample size for primary safety endpoint 1 was calculated based on the following assumptions:

Assumptions for primary safety endpoint 1

- Registry Design: nonrandomized registry
- Test basis: exact binomial test
- Type I error (alpha): 0.025 (one-sided for superiority)
- Statistical power: 80%
- Estimated AE-Free Rate at 5 years: 95.0% for Plexa leads
- Performance goal for AE-Free Rate at 5 years: 92.5%

For primary safety endpoint 1, a total of 750 evaluable Plexa leads would be required to demonstrate superiority to an AE-free rate of 92.5%. Assuming a 10% loss to follow-up rate per year over 5 years of follow-up (average of 8.2% of original population per year), a total of 1271 ($= 750 / 0.9^5$) subjects with an ICD lead would be required to be enrolled to evaluate primary safety endpoint 1.

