3. PROTOCOL REQUIREMENTS

3.1 SUBJECT POPULATION

The investigator is responsible for screening all potential patients and selecting those who are appropriate for study inclusion. The subject selected for participation should be from the investigator's general patient population according to the inclusion and exclusion criteria described below.

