3.1.3 Inclusion Criteria

To support the objectives of this investigation, the inclusion criteria at the time of subject enrollment for this registry include the following requirements:

- Successfully implanted with a BIOTRONIK ICD or CRT-D compatible system along with the Plexa lead no more than 30 days prior to consent[†]
- Able to understand the nature of the registry and provide informed consent
- Available for follow-up visits on a regular basis at the study site for the expected 5 years of follow-up
- Accepts BIOTRONIK Home Monitoring[®] concept
- Age greater than or equal to 18 years

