3.1.4 Exclusion Criteria

To support the objectives of this investigation, the exclusion criteria at the time of subject enrollment include the following requirements:

- Enrolled in any investigational cardiac device trial
- Enrolled in BIOTRONIK's QP ExCELS lead study
- Planned cardiac surgical procedures or interventional measures within the next 6 months
- Expected to receive heart transplantation or ventricular assist device within 1 year
- Life expectancy of less than 1 year
- Patients reporting pregnancy at the time of enrollment

[†] Sponsor may approve a site specific waiver upon written request to allow enrollment prior to implant per institution's requirements.

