3.2.3 Enrollment Visit

If the patient has been determined to be eligible for the registry, informed consent must be obtained from the patient prior to initiating any registry related data collection. The consent process, including discussion of the registry, should be documented in the patient's medical record. A subject with a successfully implanted Plexa lead is considered enrolled in the registry upon signing the Informed Consent Form. The visit at which informed consent is obtained is the enrollment visit and occurs no more than 30 days after the date of implant. The system the subject has at the time of signing the Informed Consent Form will be considered the study system. Prior implanted systems will not count as part of the study and AEs will only be collected from the time of the study system implant. Subject demographics are to be obtained at the enrollment visit; however, some information may be historical if it is not available with proper source documentation.

The following data collection and reporting procedures are performed at the enrollment visit:

1. Obtain informed consent
2. Collect subject demographics (date of birth, gender, etc.)
3. Collected medical history of subject, including device implant indications
4. Obtain data from the implant procedure as outlined in Section 3.2.2
5. Perform routine device interrogation:
 - Determine ICD lead mean R-wave sensing amplitude
 - Determine ICD lead pacing threshold at 0.4 ms pulse width
 - Determine the ICD lead pacing impedance
 - Determine the ICD lead shock impedance

- If Plexa DX ICD lead, determine atrial dipole mean P-wave amplitude
- Enable BIOTRONIK Home Monitoring® (if not already enabled)
- Enable RV automatic threshold management (ATM) or RV ventricular capture control (VCC)

6. Complete all required eCRFs

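### Investigators select subjects up to 30 days after implant with no consecutive-offer rule and no count of Plexa implants, so under-enrollment of early lead problems could not be seen; the exposure is mainly in secondary endpoint 4 and small for the primary endpoint.

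*Combined protocol and SAP*

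**What the plan says.** Section 2 places identification of subjects with the investigator: "Potential subjects will be identified by the investigator from their general patient population". Section 3.1 adds: "The investigator is responsible for screening all potential patients and selecting those who are appropriate for study inclusion". Neither sentence says that every eligible recipient is to be approached.

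Consent normally comes after the implant. Section 2 states: "Informed consent and enrollment visit data collection may be obtained no more than 30 days after the date of implant". The first inclusion criterion in Section 3.1.3 has the same limit: "Successfully implanted with a BIOTRONIK ICD or CRT-D compatible system along with the Plexa lead no more than 30 days prior to consent". A footnote to that criterion gives the exception: "Sponsor may approve a site specific waiver upon written request to allow enrollment prior to implant". Section 3.2.1 has the medical history reviewed before enrollment.

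The endpoint clock starts earlier. Section 2.1.1 counts Plexa lead events from implant through 5 years. For patients who do enroll, Section 2 provides that "any adverse events since the date of the implant of the Plexa lead active at the time of consent will be collected retrospectively".

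Section 9.3.1 keeps dislodgement, high pacing threshold and failure of capture at or before 30 days out of primary endpoint 1 and secondary endpoint 1, and sends them to secondary endpoint 4. Section 9.2 counts only events adjudicated as related in the primary endpoint.

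Section 2.3 describes the sample as large enough "in order to ensure a representative and statistically meaningful sample". The eCRF list (4.2), the monitoring items (7.1) and the investigator records (11.1) name no screening or non-enrollment record. The part of Section 7 between 7.1 and 7.3, the design flowchart and the Monitoring Plan were not available for this review.

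**The concern.** Entry is decided after the endpoint clock has started, by someone who may already know how the lead is doing. Implant lead measurements exist (Section 3.2.2 collects them retrospectively, where available), and Home Monitoring can send impedance, threshold and sensing values daily (Section 1.4.2). Nobody need act in bad faith: a patient facing a revision, or thought unlikely to attend for 5 years, may simply be approached less often.

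The primary result is a single-arm rate set against a fixed 92.5%, so no control group shares and cancels such selection. Collecting earlier events retrospectively helps only for patients who enroll. The center poolability analysis in Section 2.4.4 looks only at enrolled subjects. Without a count of Plexa implants at each site, the sponsor can neither show that selection was negligible nor measure it if it was not.

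**Working it through.** **1. Reproduce the plan's sample size.** Inputs from Section 2.3: exact binomial test, one-sided alpha 0.025, power 80%, expected event-free rate 95.0%, goal 92.5%. In terms of events, the test passes if X ≤ e, where e is the largest count with P(X ≤ e | n, 0.075) ≤ 0.025.

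- At n = 750, e = 42: P(X ≤ 42 | 750, 0.075) = 0.0247 and P(X ≤ 42 | 750, 0.05) = 0.801.
- 750 is the first n to reach 80% power.
- Enrolled total: 750 / 0.9^5 = 1270.1, rounded up to 1271.

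Both stated figures reproduce.

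**2. Which early events can affect which endpoint.**

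| Early Plexa event | Primary endpoint 1 | Secondary endpoint 4 |
|---|---|---|
| Dislodgement, high threshold or capture failure, day 30 or earlier | Excluded (9.3.1) | Counted, given a qualifying intervention (9.3.2) |
| Post-implant perforation, abnormal impedance, sensing problems, fracture, insulation breach | Counted only with a qualifying intervention or lead-related death (9.3.1) and if adjudicated as related (9.2) | Not the main route |

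Not enrolling a patient with an early dislodgement therefore removes no primary event directly.

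**3. A scale for the primary endpoint.** The documents give no figure for early, non-excluded, related events missed through non-enrollment. The nearest evidence is Protego Table 3 (Section 1.3.2): perforation 1, high impedance 1, undersensing 1. That is 3/1305 = 0.23%. (This is my sum, not the 0.23% printed against the total row.) Timing is not stated, the events were reported only as possibly related, and the section adds that no secondary event was adjudicated as related. Half of 0.23% is 0.115%. GALAXY Table 1 gives perforation as 5/1997 = 0.25%, also without timing. I use 0.115% to 0.25% as an illustrative range.

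**4. Effect on the test.** Let h be the share of all implants that have such an event and are never enrolled. The rate among enrolled patients is q = (p − h) / (1 − h). The rule of at most 42 events in 750 is unchanged.

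| h (assumed) | Missing per 1271 enrolled, 1271·h/(1 − h) | q if p = 7.5% | Chance of passing | q if p = 5% | Chance of passing |
|---|---|---|---|---|---|
| 0 | 0 | 7.50% | 2.5% | 5.00% | 80.1% |
| 0.115% | 1.5 | 7.39% | 3.2% | 4.89% | 83.8% |
| 0.23% | 2.9 | 7.29% | 4.0% | 4.78% | 87.1% |
| 0.25% | 3.2 | 7.27% | 4.2% | 4.76% | 87.6% |

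**5. Secondary endpoint 4.** Protego dislodgement at or before 30 days: 7/1305 = 0.54%. If a fraction f of such patients is not enrolled, the observed rate is r(1 − f)/(1 − rf) with r = 0.536%. This gives 0.40%, 0.27% and 0.13% for f = 25%, 50% and 75%. These figures mostly restate the assumed f. They show that this endpoint would take the selection almost in full.

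**The case against.** Several points on the other side are sound.

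- **The commonest early events are outside the primary endpoint.** This stands, and it keeps the primary effect small. A reader might infer that skipping early dislodgements flatters the primary rate, or might carry the model in the working to h = 0.5% or 1.0%, where the chance of passing at the boundary is 6.8% or 16.0%. The documents do not support either step. Those values of h exceed the whole Protego count of non-excluded types, even if every one of those events were early, related and missed.
- **Direction is plausible but not shown.** Nothing in the protocol indicates that investigators avoid patients with problems. Such patients may return sooner and so have more chances to consent.
- **Secondary endpoint 4 carries no hypothesis test** (Section 2.1.2). A low rate there misdescribes early performance but changes no formal decision.
- **Absence of a log is judged on the available text only.** The Monitoring Plan was not available, and Section 11.1 has a catch-all for other records the sponsor may require. To say that no log exists anywhere would go too far.
- **The waiver allows enrollment before implant at some sites.** This limits the problem there, but it is given on request, and no comparison of the two kinds of site is planned.

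What remains is that none of these provisions requires consecutive offers, and none supplies the number of implants from which the enrolled subjects came.

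**Conclusion.** The point holds as a cheap improvement. Selection after implant, with endpoints counted from implant and no enrolled-versus-implanted count in the available text, leaves room for under-enrollment of early lead problems that the registry could not detect. The descriptive early-event rates in secondary endpoint 4 are the most exposed. For primary endpoint 1 the plausible effect is modest: from 2.5% to about 3.2% to 4.2% at a true 7.5% rate. This rests on the assumed 0.115% to 0.25% of implants affected and missed, and on 750 evaluable subjects. The true size is unknown and could be zero. The documents do not show that selection has occurred, and they do not support a claim that the primary test is seriously compromised.

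**What to change.** In Section 2, and in line with it in Sections 3.1 and 3.2.1, state that from site activation every Plexa recipient who meets Sections 3.1.3 and 3.1.4 is offered enrollment consecutively. Have each site keep a de-identified tally of all Plexa implants: enrolled yes or no, and a reason category if not. Report the enrolled fraction overall and by site in the final report.

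Word the tally to fit Section 3.2.3, which requires consent before any registry data collection begins. Counts and reason categories are easier to reconcile with that rule than individual lead findings on patients who have not consented.

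Do not add a sensitivity analysis that brings in only the non-enrolled patients with a known problem. Suppose 1271 of 2542 implants enroll purely at random and the early-event rate is 11/1305 = 0.84% (Protego dislodgement 7, high threshold 3, capture failure 1; timing given only for the 7). Each half then holds about 10.7 cases, and adding only the non-enrolled cases gives 21.4 / (1271 + 10.7) = 1.67%, twice the truth with no selection at all. Any comparison must keep all implants, with and without events, in the denominator.

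The cost is some site paperwork and IRB handling of the tally. The sample size (750 evaluable, 1271 enrolled) and the visit schedule do not change. If enrollment has already begun, the tally can start from the date of the change.
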